2.3.3. End of Trial and Follow-Up Period

Visit 19 (Week 16: Post Study Drug Telephone Assessment)

- Telephone assessment for interval histories and AEs.

Table 1. Study Assessment and Procedures

	Screening	Baseline			Treatment Period and Monitoring														FU
Visit	1	2	3	4	5	6	7	8	9	10	11	12	13	14	15	16	17	18	19
Week of Treatment	-	-4~-1	-4~-1	0	1	2	3	4	5	6	7	8	9	10	11	12	12	12	16
Day of Treatment	-	-28~-7	-28~-7	1	8	15	22	29	36	43	50	57	64	71	78	85	86-91	87-92	113
Time Window			V2 +2-7d		±7	±7	±7	±7	±7	±7	±7	±7	±7	±7	±7	±7		V16 +2-7d	±3
Visit Type	OP	OP	OP	OP	Phone	OP	Phone	OP	Phone	OP	Phone	OP	Phone	OP	Phone	OP	Phone	OP	Phone
Informed Consent / Eligibility Criteria	x																		
History & Physical Exam	x																		
Body Weight	x	x	x	x						x						x	x	x	
Waist and hip circumference	x															x			
Vital signs	x	x	x			x		x		x		x		x		x		x	
Menstrual History (in females)	x		x							x								x	
Screening Laboratory Profile	x																		
Urine Pregnancy Test (in females)		x	x	x						x						x	x	x	
Methemoglobin %				x		x		x		x		x		x			x		
Estradiol Level (in females)			x															x	
Research Labs			x	x		x		x		x		x		x			x	x	
Two Hour Safety Blood Sampling				x													x		
Two Hour HR, MAP, and BP Monitoring				x													x		
Hemoglobin & hematocrit														x					
Food Questionnaire			x														x		
Whole body DEXA Scan		x															x		
Pulse Wave Velocity		x															x		
Flow Mediated Dilation		x															x		
Carotid Intima-Media Thickness		x															x		
24-hour ABPM		x															x		
Hyperinsulinemic Euglycemic Clamp			x																x
Indirect Calorimetry			x																x
Muscle Biopsy			x																x
Exercise Testing		x															x		
Meal/snack		x	x	x													x	x	x
AE Assessment		x		x	x	x	x	x	x	x	x	x	x	x	x	x	x	x	x
Medication Compliance Review					x	x	x	x		x		x		x		x		x	
Interval History Assessment			x		x	x	x	x	x	x	x	x	x	x	x	x		x	x
Brief physical exam			x		x	x	x	x		x		x		x				x	

2.4 STUDY PROCEDURES

2.4.1 Insulin Sensitivity Assessment

Euglycemic-insulin clamp

A 4-hour hyperinsulinemic (40 mU/m²/min) -euglycemic clamp will be performed at baseline (Visit 3) and Week 12 (Visit 18) to evaluate *in vivo* insulin action in stimulating glucose disposal, oxidation, and nonoxidative disposal as described before²⁵. Briefly, HumuLIN® R regular insulin will be infused at 40 mU/m²/min. Plasma glucose will be clamped between 85-95 mg/dL with a variable rate infusion of 20% dextrose in water. The rate of glucose infusion will be adjusted based on arterialized plasma glucose measurements every 5 minutes. Rates of glucose metabolism will be determined using a non-radioactive glucose isotope dilution method based on a primed, then constant infusion of the stable isotope of D-glucose [6,6-D2] 98+% enriched (0.22 μmol•kg⁻¹, 17.6 μmol•kg⁻¹ prime). This will be continued during the insulin infusion to determine rates of systemic glucose utilization (peripheral insulin resistance) and to determine insulin suppression of hepatic glucose production (hepatic insulin resistance). The deuterium labeled glucose isotope chemical purity is provided by Isotec, Inc and is tested for sterility and pyrogenicity by the manufacturer before being shipped. The maximum amount of blood to be drawn during this test is 22 Tbsp (325 mL).

Basal substrate turnover

At the fasting/baseline and end of the euglycemic clamp, basal postabsorptive glucose and fat turnover will be evaluated using a primed-continuous intravenous infusion of [6,6-D2]glucose²⁵. Substrate oxidation will be measured by continuous indirect calorimetry (Parvomedics TrueOne, Sandy, UT).

2.4.2. Systemic Arterial Vascular Function Assessments

Prior to when vascular measurements begin, subjects will be asked to abstain from tobacco and caffeine and only to have a light breakfast that is low in fat. The subject's height and weight will be measured and BMI calculated. The studies will be performed at baseline (Visit 2) and at Week 12 (Visit 16) in a quiet, temperature-controlled clinic room in the Vascular Clinical and Translational Research Center (CTRC) at Montefiore University Hospital. The subject will be asked to rest for approximately 10 minutes before the testing so that they are in a relaxed state.

Pulse Wave Velocity (PWV)

Pulse wave velocity will be performed non-invasively using SphygmoCor machine (AtCor Medical, Sydney, Australia. Model MM3. Software version 7.1) equipped with a single tonometric transducer SPT-304.

Blood pressure, pulse, and oxygen saturation will be measured on the same side as the peripheral pulse wave sampling using an automated digital oscillometric device and an average of three readings will be recorded.

Transit distances for PWV will be assessed by surface measurements from the suprasternal notch to each pulse recording site (carotid and femoral arteries). Three ECG leads will be attached on the chest. Participants will be studied in the supine position after 10 minutes of rest. Tests will be performed in duplication and the study will take 30 minutes to conduct.

Blood velocity will be calculated from the pulse wave time difference, simultaneous ECG recording and distance between the two locations with the integral software. The results will be reported as

the Pulse Wave Velocity ($V=\text{distance}/\text{time}$), which are a composite measure of the magnitude of pulse pressure and arterial stiffness in all the conduit arteries which affects wave reflection.

Higher values indicate increased wave reflection from the periphery due to increased pulse wave pressure at stiffer arteries. Those techniques have been validated for their reproducibility and used extensively.

Carotid Intima-Media Thickness (IMT)

For assessment of early stages of atherosclerosis and cardiovascular risk, the carotid artery wall is examined to identify thickness of arterial wall constitute. Dedicated ultrasound imaging of the arterial wall produces double echogenic lines. Intima-media thickness (IMT) measurement is an averaged distance between two parallel lines representing the luminal intima and media-adventitia interface. Measurements are performed approximately two centimeters proximally to bifurcation divider at the posterior (far) vessel wall using automated edge detection software.

An ultrasound machine GE VIVID-7 (GE Healthcare, Milwaukee, WI), equipped with the high resolution 8L linear transducer will be used for imaging. Three ECG leads will be attached on the chest. A dedicated IMT setting and protocol will be used for scanning. Imaging will start with transversal carotid arteries sweep for general assessment. Longitudinal B-mode ultrasound cine-loop (5 beats) of the distal common carotid artery, optimally with bifurcation, will be taken bilaterally. Horizontal image with double lines at the end of T wave will be selected. Measurement sample box will be placed approximately two centimeters proximally to bifurcation at the posterior (far) vessel wall. Semi-automated edge detection software, which traces the luminal intima and hypoechoic boundary between media and adventitia, calculates the distance between them in fast, accurate and repeatable manner. Averaged IMT values from each side in mm will be reported. The study will take 15 minutes to conduct.

Flow Mediated Dilation (FMD)

The assessment of endothelial function via Flow Mediated Dilation (FMD) has been proposed to represent a functional bioassay for endothelium - derived NO bioavailability in humans. Vascular reactivity will be quantified noninvasively using vascular ultrasound imaging. Flow and diameter changes of the brachial artery will be assessed with Duplex ultrasound images captured by a high-resolution linear array transducer.

Blood pressure will be measured on the control arm using an automated blood pressure monitor (Model CONTEC08A) and an average of three readings will be recorded. Systolic BP <100 mmHg will be considered as cut off for performing the study.

A long 5 cm wide occlusive cuff (Hokanson SC 5) with rapid release sphygmomanometer (Hokanson DS400) will be attached to an upper forearm approximately 5 cm below an elbow. Three ECG leads will be attached on the chest and lower forearms to capture ECG. Participants will be studied in the supine position after 10 minutes of rest.

Brachial artery diameter and flow velocities will be examined by high resolution ultrasound machine GE VIVID-7 (GE Healthcare, Milwaukee, WI), equipped with the 9-L linear transducer preset on specifically dedicated scanning protocol.

Cine loop 2D baseline images at B mode (15 cycles) will be obtained at the highest optimal resolution following with spectral velocity Doppler imaging (20 cycles) with scale set approximately at 200 cm/s and sweep speed at 12.5 mm/s. The occlusion cuff will be manually

inflated to 200 mmHg (or 50 mmHg above SBP) for 5 minutes and occlusion will be controlled by spectral Doppler mode. Endothelium-dependent flow mediated vasodilation of the artery will be captured in Duplex mode immediately after the cuff deflation by spectral Doppler waveform (20 cycles) approximately at 200 cm/s and sweep speed at 12.5 mm/s. Cine loop 2D vasodilation images at B mode (15 cycles) will be captured through 3 minutes after deflation during hyperemic period. Heart rate and blood pressure will be measured once by automated blood pressure monitor (Model CONTEC08A) after testing.

Images will be saved at ultrasound machine hard drive and transferred in archive format for analysis on separate equipment. The study will take 45 minutes to complete.

2.4.3. Body Composition Assessment

Whole body DEXA (Dual Energy X-ray Absorptiometry) Scan

Body composition is very important for overall health. An excessive amount of body fat is a risk factor for heart disease, type II diabetes, and other diseases. DEXA scan is considered a gold standard for measuring bone density and regional (arms, trunk, and legs) as well as total body %fat, fat mass, bone mass, and lean mass. This regional, three compartment analysis is superior not only for an initial assessment, but also for tracking change of the total increase in muscle mass and the increase in muscle mass in the arms, trunk, and legs. A DEXA scan will take approximately 8-12 minutes in the Clinical and Translational Research Center (CTRC) at the Montefiore Hospital of UPMC and will be performed at baseline (Visit 2) and Week 12 (Visit 16).

2.4.4. Ambulatory Blood Pressure Monitor (ABPM)

This lightweight (12 oz) and compact device (~1x4.5x3.5 inches) can fit in a pant pocket or worn on a belt and attaches to a blood pressure cuff that measures blood pressure every 20 minutes during the waking hours and every 30 minutes during sleeping hours across a 24 hour time period. The ABPM will be placed at the completion of Visits 2 or 3 and 16 or 17 and worn for 24 hours. The subject will be instructed on how to remove and turn off the device at completion of the 24 hours. They will then return the device at Visit 3 or 4 and Visit 17 or 18, 2-7 days later. Verbal and written instructions will be provided to the subjects at this visit before discharge home. It can be worn to work, while sleeping and driving. The cuff and monitor should only be removed when showering/bathing or swimming.

2.4.5. Mitochondrial Function Studies

Platelet mitochondrial studies

In these studies, fresh platelets will be isolated from the blood and mitochondrial function and platelet activation measured. The analyses of mitochondrial function and platelet activation will potentially provide mechanistic information about the metabolic and thrombotic state of the patients at baseline as well as information about the mechanism by which nitrite modulate vascular and mitochondrial function in the subjects.

At Visits 4 and 17, 8 mL each of blood will be taken at time 0, 0.5 and 2 hours (24mL total per visit) and will be used for platelet isolation and measurement of mitochondrial function. Fresh platelets will be isolated and analyzed by extracellular flux analysis and platelet activation by flow cytometry in the lab of affiliated investigator, [name], at the University of Pittsburgh. A single sample will also be collected at Visit 10 (week 6) to examine the temporal relationship of whether there is a dissipating effect over time on platelet mitochondrial function.

Muscle mitochondrial studies

Percutaneous muscle biopsy: The muscle biopsy will be performed early in the morning of Visit 3 and Visit 18. The biopsy site will be monitored over 6 hours until completion of all of the visit testing. An ice pack will be applied for 20 minutes after the biopsy. The subject will be given instructions about how to care for the incision site and provided with the telephone numbers of the investigators to call if they have any problems.

The EMRC group has performed more than 800 muscle biopsies during the past 16 years, and more than 200 just in the past year. In the CTRC on the morning prior to the glucose clamp, i.e., during fasting conditions, a percutaneous muscle biopsy of the vastus lateralis will be performed. High-resolution respirometry: Mitochondrial respiratory capacity will be measured in permeabilized muscle fibers from vastus lateralis muscle biopsies (Oroboros Oxygraph 2K, Innsbruck, Austria). The instrument has two chambers, which permits high-resolution respiration measurements to be made in duplicate with low amounts of muscle tissue (2mg). The O₂K assay allows a comprehensive evaluation of mitochondrial respiratory function upon titration with electron transport chain (ETC) complex-specific inhibitors and substrates^{28,29}. Measurement of H₂O₂ emission by mitochondria will be measured from permeabilized muscle fiber bundles by real time monitoring of Amplex Red oxidation using HPLC detection³⁰. Maximal State 3 (coupled) respiration and maximal State 4 (uncoupled) respiration will be measured as the primary mitochondrial function parameters. As a measure of mitochondria inner membrane content in muscle biopsies, we will measure cardiolipin content; a phospholipid unique to mitochondrial inner membrane. A HPLC assay with fluorescence labeling will be used for measurements of the content and specific species of cardiolipin as an index of mitochondrial remodeling, in <10mg of biopsy material.

2.4.6 Exercise Testing

Subjects will perform an exercise test on a stationary bicycle ergometer (Lode Excaliber, Gronigen, The Netherlands) in the Exercise Physiology Laboratory in the EMRC. The test will begin with a warm-up of light pedaling. Then each subject will perform two, 4-min standardized workloads of 25 and 50 Watts so that steady-state VO₂ can be achieved. This will provide important information about whole body metabolic efficiency that may be linked with the intervention. After the submaximal workloads are completed, they will continue with 2-min stages of incrementally greater workloads of 25 Watts until a maximal voluntary effort is attained to assess maximal O₂ consumption as a measure of maximal cardiorespiratory fitness. The EMRC has performed similar tests in more than 1,000 volunteers ranging from elderly women in their 80's to highly trained athletes.

2.4.7. Laboratory Profiles

Basic Laboratory Profiles

Basic laboratory profile of peripheral blood will be analyzed through the clinical laboratories at Presbyterian Hospital of UPMC clinical automated testing lab and at Esoterix. Presbyterian Hospital of UPMC testing will include:

- Triglycerides, HDL, fasting glucose, TSH, hemoglobin and hematocrit at screening (Visit 1)
- CBC, creatinine, AST and ALT at baseline assessment visit (Visit 3)
- HbA1C and lipid profile at baseline assessment visit (Visit 3) and week 12 follow-up assessment visit (Visit 18)
- Methemoglobin % by co-oximetry (Visits 4 through 15 and 17)

Esoterix testing (in females) will include estradiol at baseline assessment visit (Visit 3) and week 12 follow-up assessment visit (Visit 18).

Research Laboratory Profiles

Samples will be analyzed for nitrite and nitrate by gas phase ozone-based chemiluminescence detection²⁷. Blood samples will be processed and analyzed in the Core NO (Nitric Oxide) Metabolomics Facility at the University of Pittsburgh, under the supervision of the Sponsor, [name].

Fasting laboratory testing at baseline (Visit 3) and week 12 follow-up assessment visit (Visit 18) will include hsCRP, uric acid, ICAM-1, VCAM-1, e-Selectin, adiponectin, leptin, PAI-1, IL-6, and TNF- α for a total of approximately 2 Tablespoons (30 mL).

2.4.8. 72 hour dietary food recall

Subjects will be asked to complete dietary food recalls of the prior 72 hours. These will be collected at baseline visit (Visit 3) and week 12 follow-up visit (Visit 15 or 16) to assess for dietary nitrate and nitrite consumption.

2.5 STUDY ENDPOINTS

2.5.1 Primary End-Points

Primary outcome measure: change in insulin sensitivity (ie. insulin stimulated glucose disposal) by hyperinsulinemic euglycemic clamp

2.5.2. Secondary End-Points

Secondary outcome measures:

1. Change in systolic, diastolic and mean arterial pressures from baseline to 12 weeks
2. Change in muscle and platelet reactive oxygen species (ROS) generation, mitochondrial efficiency, and uncoupling in platelet and muscle biopsy sample studies
3. Change in endothelial function by flow mediated dilation (FMD)
4. Change in body weight
5. Change in arterial stiffening by carotid-femoral pulse wave velocity (PWV)
6. Change in arterial (intimal) thickening by intima-media thickness (IMT)
7. Change in HbA1C
8. Change in blood markers of inflammation, and vascular dysfunction: ICAM-1, VCAM-1, e-Selectin, CRP, PAI-1, IL-6, TNF- α , lipid profile, adiponectin, and leptin
9. Change in substrate oxidation by indirect calorimetry
10. Change in cardiorespiratory fitness by maximal exercise tolerance test
11. Change in body composition by whole body DEXA for total body fat
12. Safety monitoring with every other week methemoglobin by co-oximetry and PK obtained plasma nitrate and nitrite concentrations by chemiluminescence and red cell iron-nitrosyl-hemoglobin

2.6 STATISTICAL ANALYSIS

Primary endpoint sample size estimates: To develop sample size estimates, we hypothesize that inorganic nitrite will have significant but perhaps slightly less robust effects compared to a 4-month supervised exercise weight loss intervention. We anticipate an effect size (improvement) in insulin stimulated glucose uptake of ~ 1.68 mg/min/kg fat free mass (FFM) with dietary nitrite. This represents just 60% of the effect size we have observed with diet and exercise (based on a mean

improvement in insulin sensitivity from 6.70 ± 2.0 (SD) to 9.51 ± 2.5 mg/min/kg FFM; n=25). This would provide 80% power to detect this conservatively-estimated smaller effect size in 30 subjects at a p value of 0.05.

Primary and secondary endpoint analyses: Repeated measures ANOVA with visit (pre-, post-treatment) as the within-subject effect will be used to evaluate response to treatment for primary and secondary endpoint measures of insulin sensitivity, mitochondrial function (muscle and platelet ROS generation, mitochondrial efficiency, and uncoupling by various platelet and muscle biopsy samples), BP, methemoglobin %, endothelial function (FMD), body weight, arterial stiffening (PWV), arterial thickening (IMT), glucose tolerance (HbA1C), blood markers of inflammation and vascular dysfunction, substrate oxidation (indirect calorimetry), cardiorespiratory fitness (maximal exercise tolerance test), and body composition (whole body DEXA for total body fat). Data will be presented as the mean \pm standard error for continuous variables. Transformations will be considered for data demonstrating non-normal distributions.

An interim statistical analysis is planned following completion of the 10th subject. If there is a statistically significant change in the primary outcome measure of insulin sensitivity with $p < 0.001$, discontinuation of the trial will occur. If $p > 0.001$, the trial will continue. Based on an extremely low p value to stop the trial, there will be no need to adjust final significance level.

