1.2 SPECIFIC AIMS

Hypothesis:

Oral supplementation with sodium nitrite will result in improvement in insulin sensitivity, reduction in blood pressure, and improvement in endothelial and mitochondrial function, arterial stiffening, and microvascular inflammation, in overweight/obese adult subjects with metabolic syndrome and hypertension with limited toxicity in the dose proposed.

Specific Aims:

Aim 1: To examine the effect of oral nitrite on insulin sensitivity and mitochondrial function in overweight/obese adults with metabolic syndrome and hypertension.

Aim 2: To examine the effect of oral nitrite on blood pressure in overweight/obese adults with metabolic syndrome and hypertension.

Aim 3: To examine the effect of oral nitrite on endothelial function, arterial stiffening, and microvascular inflammation in overweight/obese adults with metabolic syndrome and hypertension.

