Based on the above PK and the differential BP effects with single doses of sodium nitrate vs. nitrite, the published 10-week oral nitrite trial and preliminary findings in this combined trial, we propose to remove sodium nitrate, which is the second potential depot of nitrite. Therefore, we need to administer a greater nitrite load since the previous two sources combined (sodium nitrate and nitrite) in the first 5 subjects of this study did not result in any BP lowering (Fig 1A-C). Similar to our prior dosing modification (when we titrated from sodium nitrite 20 mg once daily to 20 mg twice daily), we propose a step-up dosing in the first 3 subjects enrolled whereby we will begin with sodium nitrite 20 mg TID daily and after 2 weeks on this dosing and if no SAE, increase to 40 mg TID for the remaining 10 weeks of the study, given the PK of the drug and to induce blood pressure lowering in our hypertensive subjects. After three subjects have completed this regimen, then we propose that from the start, all remaining subjects start on sodium nitrite 40 mg TID and continue for all 12 weeks.

Although we are increasing the dose/frequency of sodium nitrite, since we are discontinuing sodium nitrate (which is reduced to nitrite in our body as was confirmed in our Phase I PK study), we are continuing our in-person safety monitoring visits to assess for adverse events at every other week. We will continue alternating every other week phone visits to assess compliance and for adverse events. Our two safety outcomes are methemoglobin by non-invasive co-oximetry and mean arterial pressure (MAP) obtained through 3 automated resting BP measurements 30-45 min following morning nitrite dosing and averaging the final 2 of 3 MAPs.

Based on the Joint FAO/WHO ADI for sodium nitrate and nitrite, the above DASH diet patterns, and the recently observed human and rodent effects of nitrate and nitrite on blood pressure and

glucose homeostasis, including our PK/PD trial of single doses of oral nitrate and nitrite, the existing inhaled nitrite trial, and this open label trial safety and lack of BP reduction findings following a total of 5 subjects' completion, the study investigators believe that a safe and likely therapeutically effective dose of sodium nitrite will be 40 mg three times daily (~1.26 mg/kg body weight per day for a 95 kg subject). Our sodium nitrite dose selection is equivalent to 12.6 times the ADI.

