There is a rare possibility that a subject will have a high methemoglobin level or will have a low blood pressure from their study drug dose during this visit or future study visits. If this happens, their study nitrite drug dose will be lowered so that they receive half the dose of the nitrite (20 mg sodium nitrite three times daily). They will be asked to undergo a repeat of safety monitoring for blood pressure, breathing rate and heart rate before taking the medicines and then every 15 minutes for 2 hours after taking the study medications, methemoglobin level by a finger probe, research blood and storage samples and blood samples for platelet mitochondrial function that will be drawn before, 0.5, 1 and 2 hours after the lowered dose of study medication are administered (as above). The total volume of blood drawn is approximately 3 Tablespoons. If they still have a high methemoglobin or low blood pressure on the lower dose, their participation in the study will be discontinued.

Visits 5-15 (Weeks 1 through 11):

Participants will have every other week in-person EMRC safety visits and phone visits on alternate weeks, starting with week 1 (Visit 5) if no dose limiting adverse events occur (as defined in protocol based on MAP and MetHb levels). Phone visits will take place on Visit 5, 7, 9, 11, 13 and 15.

During Visits 6, 8, 10, 12, and 14 (Weeks 2, 4, 6, 8, and 10 on study drug), the subjects will return every other week \pm 7 days to the EMRC in Montefiore Hospital of UPMC for a safety visit, which will take approximately 1-1 ½ hours for:

- Subjects will be seated in the EMRC and given their daily dose of morning study drug or second/midday dose (depending on time of scheduled visit)
- Brief physical exam
- 0.5 hours after taking their study drug, 3 automated blood pressure, HR and MAP measurements will be taken by the subject with 5 minutes intervals between measurements
- Assess adverse events (AE) and medication compliance
- Obtain methemoglobin by co-oximetry and research blood for plasma nitrate and nitrite levels and a sample for storage
- Provide a 14 +/- 3 day supply of study drug

During Visits 5, 7, 9, 11, 13, and 15 (Weeks 1, 3, 5, 7, 9, and 11 on study drug or every other week), we will contact the subject by phone for a safety visit to assess interval histories and assessment of adverse events (AE), which will last about 10 minutes.

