- The frequency of monitoring that took place during the renewal intervals and/or the dates that data and safety monitoring was conducted.
- A summary of cumulative data related to unanticipated problems (including adverse events) including a determination of causality and whether the risk to benefit assessment has changed.
- If appropriate, a summary of pertinent scientific literature reports, therapeutic developments, or results of related studies that may have an impact on the safety of study participants or the ethics of the research study.
- A summary of the outcome of reviews conducted to ensure subject privacy and research data confidentiality.
- Final conclusions regarding changes to the anticipated benefit-to-risk assessment of the study participation and final recommendations related to continuing, changing, or terminating the study.

Stopping Rule:

For safety reasons, we propose to discontinue this study protocol once 2 subjects enrolled experience one of two of the following on repeat PK testing despite appropriate nitrite dose reduction as follows:

1. Methemoglobin greater than 5%. A nitrite dose reduction is proposed from 40 mg three times daily to 20 mg three times daily if this methemoglobin % is reached at any study visit. Two hour PK testing will be repeated on a separate day at the lower nitrite dose once two subjects have reached this initial methemoglobin threshold. If methemoglobin is greater than 5% on the lower nitrite dose, participation in the study for the subject will be discontinued.
2. Mean arterial pressure (MAP) decrease <55 mmHg, or if subject's baseline MAP is <60, and there is a decrease greater than or equal to 20% from their baseline (on the morning of receiving study drug). A nitrite dose reduction is proposed from 40 mg to 20 mg three times daily if this MAP threshold is reached. Two hour PK testing will be repeated on a separate day at the lower nitrite dose once two subjects have reached this initial MAP threshold. If MAP remains <55 mmHg or in the case of the subject with a baseline MAP <60, then if MAP decrease is greater than or equal to 20% from baseline on the lower dose, subject participation in the study will be discontinued.
3. Positive pregnancy test.

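### Section 2.6 summarises methemoglobin, a declared safety outcome, only by a pre/post mean; no per-subject maximum or count above the trial's own 5% limit is planned for the results

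*Combined protocol and SAP*

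**What the plan says.** Section 2.2.2 states: "Our two safety outcomes are methemoglobin by non-invasive co-oximetry and mean arterial pressure (MAP", and goes on to describe how MAP is obtained. Section 2.5.2 lists, as secondary endpoint 12, "Safety monitoring with every other week methemoglobin by co-oximetry and PK obtained plasma nitrate and nitrite concentrations". The hypothesis in Section 1.2 expects benefit "with limited toxicity in the dose proposed".

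Section 2.6 gives the analysis: "Repeated measures ANOVA with visit (pre-, post-treatment) as the within-subject effect will be used to evaluate response to treatment". Methemoglobin % and BP are both in the list of measures that follows, and continuous data are to be shown as mean and standard error. The section mentions no maximum, count, proportion or listing for either safety outcome. It also does not say how withdrawn subjects are handled.

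The 5% limit appears in Section 5.4.2 as a conduct rule. A subject above it has the dose reduced, as Section 2.3.2 also says: "If this happens, their study nitrite drug dose will be lowered so that they receive half the dose of the nitrite". On the lower dose, "If methemoglobin is greater than 5% on the lower nitrite dose, participation in the study for the subject will be discontinued". The study stops "once 2 subjects enrolled experience one of two of the following on repeat PK testing despite appropriate nitrite dose reduction". Section 5.4.2 sets a corresponding MAP threshold.

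**The concern.** The trial's own rule for methemoglobin acts on individual readings, and Section 5.1.1 describes harm in terms of an individual's level. A mean change answers a different question. It can stay close to zero while one or two subjects cross the limit.

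The Week 12 value is also measured after the safety rule has acted. A subject who exceeds 5% and settles on the lower dose contributes a lower-dose reading. The contrast therefore mixes doses, in a direction that tends to look favourable, although the hypothesis concerns the proposed dose. At stake is whether the results can support the toxicity part of the hypothesis; the primary endpoint is not affected.

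**Working it through.** Section 2.6 states no figure for methemoglobin, so there is none to reproduce. Its only computed figure, power for insulin sensitivity, does not bear on this point.

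**1. Readings and the planned contrast** (Sections 2.3.2 and 2.3.3, Table 1)
- Visits 4 and 17: 0, 0.5, 1 and 2 hours, so 2 × 4 = 8 readings.
- Visits 6, 8, 10, 12 and 14: one each, so 5 readings.
- Total: 13 readings at 7 visits. A pre/post contrast draws on at most Visits 4 and 17, which leaves 5 of 7 visits without a stated analysis.
- The only reading before any drug is 0 hours at Visit 4. Section 2.6 does not say which Visit 17 time point is set against it. The choice could matter: Section 2.2.2 reports plasma nitrite peaking at 30 minutes and back at baseline between 3 and 6 hours, and the 0-hour reading at Visit 17 is a trough.

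**2. Effect of dose reduction on the mean** (assumed: pre value 1%, peak 6%; the 1–3% background range is from Section 5.1.1)
- If the 6% reading were the Week 12 value: (6 − 1)/30 = 0.17 points on the mean.
- If that subject is dose-reduced and back at 1–3% by Week 12: (1 − 1)/30 to (3 − 1)/30 = 0 to 0.07 points.

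**3. What the paired test shows** (assumed: k of n = 30 subjects rise by the same amount d, the rest do not change)
- Mean change = kd/n; SE = (d/n)·√[k(n − k)/(n − 1)]; so t = √[k(n − 1)/(n − k)], on 29 df. The size of the rise cancels.
- k = 1: t = √(29/29) = 1.00, p = 0.33.
- k = 2: t = √(58/28) = 1.44, p = 0.16.
- k = 3: t = √(87/27) = 1.80, p = 0.083.

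**4. What a count would show** (Clopper-Pearson 95% intervals, n = 30)

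| Subjects ever above 5% | Percentage | Exact 95% CI |
|---|---|---|
| 0/30 | 0% | 0 to 11.6% |
| 1/30 | 3.3% | 0.1 to 17.2% |
| 2/30 | 6.7% | 0.8 to 22.1% |

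For 0/30 the upper limit is 1 − 0.025^(1/30) = 0.116.

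**5. Chance of seeing at least one exceedance**, 1 − (1 − p)^30, with p assumed because the documents give no rate
- p = 1%: 1 − 0.99^30 = 26%
- p = 2%: 1 − 0.98^30 = 45%
- p = 5%: 1 − 0.95^30 = 79%
- p = 10%: 1 − 0.90^30 = 96%

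The low end deserves weight. Section 5.1.1 reports no level above 3% in 80 volunteers at doses under 75 mg, and 0/80 has an exact upper limit of 1 − 0.025^(1/80) = 4.5%. Exposure and population differ, so this is only indicative.

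**The case against.** The strongest reply is that an exceedance cannot hide behind a mean in this trial. Section 2.3.2 treats the MAP and methemoglobin limits as dose-limiting adverse events. Sections 5.4.2 and 5.4.3 require adverse events to be recorded for each participant, summarised for the DSMB and reviewed. Section 5.4.2 acts on each subject above 5%, and its timing of repeat testing implies that first exceedances are also tracked. All of this stands. A reader might infer that high readings would go unnoticed or that subjects are unprotected; the documents do not support that. What these provisions do not set is a summary of exceedances in the trial's results. The study-stopping count covers only repeat testing after dose reduction.

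A second reply is that repeated measures ANOVA can take several post-treatment visits, and that the pre/post wording is shared by about a dozen measures. That is fair. A reader might infer that the model excludes Visits 6 to 14, but the text shows only that their use is unstated. Adding those visits would still yield means.

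Third, the single-subject test result requires the other 29 changes to be exactly zero, and a very large rise would show itself clinically. This also stands: the calculation illustrates what the test is insensitive to and does not predict the data.

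Finally, a count from 30 subjects is imprecise. At true rates of 1% or 2% it would more often than not be 0/30, with an upper limit of 11.6%, which is weak support for limited toxicity. That limits what the trial can claim under either summary, and the interval makes the limit visible.

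**Conclusion.** The point holds as a gap in the planned outcome analysis. The pre/post mean leaves five of seven methemoglobin visits without a stated use, does not name its time points, and takes reduced-dose Week 12 values from any subject whose dose was halved. It is a poor basis for judging toxicity at the proposed dose. The direction towards reassurance follows from the dose-reduction rule; its size depends on how many subjects are reduced and cannot be known in advance. In the illustration, one subject's contribution falls from 0.17 to between 0 and 0.07 points.

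MAP, the other declared safety outcome, has the same gap: BP is in the same ANOVA, with no per-subject summary against the Section 5.4.2 threshold.

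A reader might go further and infer that the drug is likely to breach the limit. Nothing in the documents shows this; the earlier experience in Sections 2.2.2 and 5.1.1 points the other way. The primary endpoint and sample size are unaffected. The illustrative methemoglobin values, the unchanged remaining subjects and the true exceedance rates are assumptions.

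**What to change.** In Section 2.6, for all subjects who took at least one dose, including dose-reduced and withdrawn subjects:

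- Report each subject's maximum methemoglobin over all scheduled and repeat-PK readings from the first dose onward, with the dose at that time. Dose is needed in any case because Section 2.2.2 starts the first three subjects on a step-up regimen.
- Report the number and percentage ever above 5%, with an exact 95% CI.
- Keep the pre/post mean as descriptive, and name the Visit 4 and Visit 17 time points it uses.
- Give the same per-subject summary for MAP against the threshold already in Section 5.4.2.

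The cost is SAP wording and one table from data already scheduled. The downsides are the wide interval and a possible understatement of the peak: Section 2.3.2 times blood pressure at Visits 6 to 14 but gives no post-dose time for methemoglobin. Recording that time would help, but it is a new data item and a separate cost.

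Separately, correct the protocol's visit list. Section 2.4.7 places methemoglobin at Visits 4 through 15 and 17, whereas Section 2.3.2 says "Phone visits will take place on Visit 5, 7, 9, 11, 13 and 15", and Table 1 shows no methemoglobin reading at those visits. These need to be reconciled.
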